- Turn off the RX-0201 infusion pump, disconnect the infusion bag and record the volume infused during the past 7 days in the subject's medical record and eCRF, if applicable.

7.6 Cycles 1 to n, Days 18-21 – Imaging Assessment – Stage 2

- Disease assessment will occur at the end of Cycles 2, 4, 6, 8, ... n (i.e., after every 6 weeks of therapy).
- Radiological imaging to assess disease extent. Radiological assessment must include CT scan or MRI of the abdomen and pelvis and the modality selected should be the same throughout the study. The results of the imaging assessment must be available

and reviewed before the start of the next cycle. Some imaging assessments may be collected for a second review by a central imaging vendor.

- Disease assessment should be conducted according to the RECIST ver. 1.1 guidelines modified as described in Appendix E.
- Blood collection for biomarker sample analysis within 1 day of tumor assessment

7.7 Unscheduled Visit(s) – Stage 1 and Stage 2

An unscheduled visit may be performed at any time during the study at the request of the subject or as deemed necessary by the investigator. The date and reason for the unscheduled visit will be documented in the subject's medical record and eCRF, as well as any other data obtained (e.g., adverse events, concomitant medications and treatments, and results from procedures or tests).

7.8 End of Treatment or Early Termination Visit - Stage 1 and Stage 2

The following procedures will be performed:

- Record concomitant medication(s)
- Record adverse event(s). Serious adverse events will be reported immediately. Any adverse event that is considered related to study drug(s) will be followed to resolution or return to baseline.
- ECOG performance status
- Vital signs: resting pulse, resting respiration rate, resting blood pressure (i.e., after the subject has been seated for at least 5 minutes) and temperature measurements.
- Everolimus compliance – Record the number of tablets taken at home since the last visit.
- Laboratory tests
 - Urinalysis
 - Hematology panel
 - Chemistry panel
 - Coagulation
 - Pregnancy test (if applicable, urine or serum)

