9.2.2 Analysis Populations

Data from stages 1 and 2 of this study will be combined for both safety and efficacy analyses when appropriate. The following definitions of the various analysis sets to be used will therefore be applied to subjects in Stage 1 and Stage 2 of the study.

Safety Analysis Set:

The safety analysis set includes all subjects who receive at least one dose of study drug(s) with subjects analyzed according to the treatment received. All safety data will be analyzed in accordance with this analysis set.

Full Analysis Set:

The Full Analysis set includes all enrolled or randomized subjects with subjects analyzed according to the treatment assigned at enrollment/randomization. All efficacy endpoints will be analyzed using the Full Analysis set.

Per Protocol Analysis Set:

The Per-Protocol Analysis set will include all subjects without pre-specified major protocol deviations. Sensitivity analyses of some efficacy endpoints may be performed using the per-protocol analysis set.

Evaluable for Tumor Response Analysis Set (Stage 2 only):

The tumor response analysis set will include all subjects in the Full Analysis Set (and Per-Protocol Set if applicable) with a uni-dimensional measurable lesion at baseline (as per RECIST ver. 1.1).

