Appendix E. RECIST ver. 1.1

(Eisenhauer, E. A., et al., 2009)

Definitions

- **Measurable Disease** - the presence of at least one measurable lesion. If the measurable disease is restricted to a solitary lesion, its neoplastic nature should be confirmed by cytology/histology.
 - **Measurable Lesions** - lesions must be accurately measured in at least one dimension (longest diameter in the plane of measurement is to be recorded) with a minimum size of 10 mm by CT scan (irrespective of scanner type) and MRI (no less than double the slice thickness and a minimum of 10mm); 10mm caliper measurement by clinical exam (when superficial); or 20 mm by chest X-ray (if clearly defined and surrounded by aerated lung).
 - **Non-measurable Lesions** - all other lesions, including small lesions (longest diameter <20 mm with conventional techniques or <10 mm with spiral CT scan), ie, leptomeningeal disease, ascites, pleural/pericardial effusion, inflammatory breast disease, lymphangitic involvement of the skin or lung, and also abdominal masses/ abdominal organomegaly identified by physical exam that is not measurable by reproducible imaging techniques. Lytic bone lesions, with an identifiable soft tissue component, evaluated by CT or MRI, can be considered as measurable lesions if the soft tissue component otherwise meets the definition of measurability previously described. Blastic bone lesions are non-measurable.
- All measurements should be taken and recorded in metric notation, using a ruler or calipers. All baseline evaluations should be performed as closely as possible to the beginning of treatment and not more than 21 days before study day 1.
 - The same method of assessment and the same technique should be used to characterize each identified and reported lesion throughout the trial.
 - Clinical lesions will only be considered measurable when they are superficial (eg, skin nodules and palpable lymph nodes) and ≥ 10 mm in diameter as assessed using calipers. For the case of skin lesions, documentation by color photography, including a ruler to estimate the size of the lesion, is recommended.

Methods of Measurement

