- CT is the best currently available and reproducible method to measure lesions selected for response assessment. MRI is also acceptable in certain situations (e.g. for body scans but not for lung). CT and MRI should be performed with cuts of 5 mm or less in slice thickness contiguously. When CT scans have a slice thickness >5 mm, the minimum size should be twice the slice thickness. Spiral CT should be performed using a 5 to 8 mm contiguous reconstruction algorithm. This applies to tumors of the chest, abdomen and pelvis. Head and neck tumors and those of extremities usually require specific protocols.
- Ultrasound should not be used to measure tumor lesions.
- Cytology and histology can be used to differentiate between partial response and complete response in rare cases (eg, after treatment to differentiate between residual benign lesions and residual malignant lesions in tumor types such as germ cell tumors).

Baseline Documentation of “Target” and “Non-Target” Lesions

- All measurable lesions up to a maximum of two lesions per organ and five lesions in total, representative of all involved organs should be identified as **target lesions** and recorded and measured during screening.
- It may be the case that, on occasion, the largest lesion does not lend itself to reproducible measurement in which circumstance the next largest lesion which can be measured reproducibly should be selected.
- A sum of the diameters (longest for non-nodal lesions, short axis for nodal lesions) for all target lesions will be calculated and reported as the baseline sum diameters. The baseline sum diameters will be used as reference by which to characterize any objective tumor regression in the measurable dimension of the disease. If lymph nodes are to be included in the sum, only the short axis will contribute. All other lesions (or sites of disease) should be identified as non-target lesions and should also be recorded during screening. Measurements of these lesions are not required, but the presence or absence of each should be noted throughout the study. It is possible to record multiple nontarget lesions involving the same organ as a single item on the eCRF (e.g. “multiple enlarged pelvic lymph nodes” or “multiple liver metastases”).

Subsequent Documentation of “Target” and “Non-Target” Lesions

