- All target lesions (nodal and non-nodal) recorded at baseline should have their actual measurements recorded at each subsequent evaluation, even when very small (e.g. 2mm). However, if target lesions or lymph nodes become so faint on CT scan that the radiologist may not feel comfortable assigning an exact measure and may report them as being ‘too small to measure’, a default value of 5mm should be assigned
- When non-nodal lesions ‘fragment’, the longest diameters of the fragmented portions should be added together to calculate the target lesion sum. Similarly, as lesions coalesce, a plane between them may be maintained that would aid in obtaining maximal diameter measurements of each individual lesion. If the lesions have truly coalesced such that they are no longer separable, the vector of the longest diameter in this instance should be the maximal longest diameter for the ‘coalesced lesion’
- Finding of a new lesion should be unequivocal: i.e. not attributable to differences in scanning technique, change in imaging modality or findings thought to represent something other than tumor. This is particularly important when patient’s baseline lesions show PR or CR. When in doubt, subsequent timepoint should be evaluated. Lesion seen in anatomical region which was not imaged at baseline = new lesion

Response Criteria

Evaluation of Target Lesions

- * Complete Response (CR): Disappearance of all target lesions. Any pathological lymph nodes (whether target or non-target) must have reduction in short axis to <10 mm.
- * Partial Response (PR): At least a 30% decrease in the sum of the diameters of target lesions, taking as reference the baseline sum of diameters.

- * Progressive Disease (PD): At least a 20% increase in the sum of the diameters of target lesions, taking as reference the smallest sum recorded since the treatment started (nadir). The sum must also demonstrate an absolute increase of at least 5 mm over nadir.
- * Stable Disease (SD): Neither sufficient shrinkage to qualify for PR nor sufficient increase to qualify for progressive disease.

Evaluation of Non-Target Lesions

- * Complete Response (CR): Disappearance of all non-target lesions and normalization of tumor marker levels. All lymph nodes must be non-pathological in size (<10 mm short axis).
- * Non-CR/ Non-PD: Persistence of one or more non-target lesion(s) and/or maintenance of tumor marker levels above normal limits.

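### Appendix E sets conflicting minimum sizes for a measurable lesion and no short-axis entry size for lymph nodes, which leaves membership of the tumor response set and some responses open to interpretation

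*Protocol*

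**What the plan says.** Protocol Section 7.6 makes the appendix the working text: "Disease assessment should be conducted according to the RECIST ver. 1.1 guidelines modified as described in Appendix E". The SAP gives no lesion sizes of its own; Section 4.3 refers to Appendix E for the criteria.

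**Size.** Under Definitions, Appendix E accepts lesions "with a minimum size of 10 mm by CT scan (irrespective of scanner type) and MRI", sets 10 mm for calipers and 20 mm for chest X-ray, and for MRI also requires at least double the slice thickness. The following bullet classes as non-measurable all remaining lesions, including small ones with "longest diameter <20 mm with conventional techniques or <10 mm with spiral CT scan".

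**Slice thickness.** Under Methods of Measurement, CT and MRI cuts are to be 5 mm or less. The same bullet adds: "When CT scans have a slice thickness >5 mm, the minimum size should be twice the slice thickness". It then says: "Spiral CT should be performed using a 5 to 8 mm contiguous reconstruction algorithm".

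**Nodes.** Measurability is judged on longest diameter, and palpable nodes count from 10 mm diameter by calipers. Only the short axis of a node enters the sum. For complete response, pathological nodes "must have reduction in short axis to <10 mm", and the non-target criteria describe nodes below that size as non-pathological. No sentence gives a short-axis minimum for choosing a node as a target.

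**Use.** Protocol Section 9.2.2 limits the Evaluable for Tumor Response set to subjects "with a uni-dimensional measurable lesion at baseline (as per RECIST ver. 1.1"). Section 9.5.2.4 excludes subjects without such a lesion from the response analyses.

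**The concern.** Two sites following Appendix E in good faith can classify the same lesion differently. For a subject whose lesions all lie in the disputed size range, that decides two things: whether the subject is in the response set, and whether time-point response is read from Table 1 of SAP Section 4.3 (target lesions, with partial response and stable disease available) or from Table 2 (non-target only, with neither category).

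The nodal gap works differently. It admits as a target a node that Appendix E itself regards as normal in size, so a small change in a normal-sized structure can count as tumor shrinkage. At stake are response rate, time to response and duration of response, the Stage 2 secondary efficacy endpoints, in an arm of up to 20 subjects.

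**Working it through.** There is no planned figure to reproduce. The check sets the rules side by side and then sizes the effect.

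**1. Where the size rules disagree** (all inputs from Appendix E)

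| Technique | Accepting rule | Rejecting rule | Disputed range |
|---|---|---|---|
| Non-spiral CT, slices up to 5 mm | 10 mm or more | under 20 mm, if conventional | 10 to <20 mm |
| MRI, slices up to 5 mm | 10 mm or more | under 20 mm, if conventional | 10 to <20 mm |
| Calipers | 10 mm or more | under 20 mm, if conventional | 10 to <20 mm |
| Chest X-ray | 20 mm or more | under 20 mm | none |
| Spiral CT, 5 mm | 10 mm or more | under 10 mm | none |
| Spiral CT, 8 mm | 10 mm or more | under 2 x 8 = 16 mm | 10 to <16 mm |

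The first three rows depend on whether the undefined term covers those techniques. In the last row the minimum scales with thickness: at 6 mm it is 2 x 6 = 12 mm, so a 12 mm lesion fails only when slices exceed 6 mm.

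**2. The node** (assumed example: 14 mm long axis, 9 mm short axis)

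- Entry: 14 mm is at least 10 mm, so it can be a target.
- Baseline sum if it is the only target: 9 mm.
- Normal by Appendix E's own figure: 9 mm is under 10 mm.
- Partial response needs a fall of at least 30%. From 9 to 6 mm is 3/9 = 33%, which qualifies. If the node is reported as too small to measure, the 5 mm default gives 4/9 = 44%.
- No change: 0/9 = 0%, so no partial response.

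**3. Effect on the response rate** (response taken as confirmed complete or partial response; 4 responders among 20 is an assumption)

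- Start: 4/20 = 20.0%, exact 95% interval 5.7% to 43.7%.
- One non-responder falsely scored as a responder: 5/20 = 25.0%, +5.0 points.
- One non-responder removed from the set: 4/19 = 21.1%, +1.1 points.
- One responder removed: 3/19 = 15.8%, -4.2 points.
- Two non-responders removed: 4/18 = 22.2%, interval 6.4% to 47.6%.
- Two responders and two non-responders removed: 2/16 = 12.5%, interval 1.6% to 38.3%.

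**The case against.** The strongest reply is that the text can be read coherently. Non-measurable is a residual class, so the 10 mm rule could be taken to prevail. If conventional techniques means chest X-ray, the 20 mm figure agrees with the bullet above it. The twice-slice-thickness rule is a qualifier for thick slices rather than a contradiction. The complete-response clause speaks of pathological nodes, which hints that smaller nodes are not disease. A solitary measurable lesion should be confirmed by cytology or histology, and responses need confirmation.

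Part of this stands: the slice rule is sound and should stay. The rest does not settle the matter. Singling out spiral CT at 10 mm implies another limit for other CT, against the statement that scanner type is irrelevant. The 5 to 8 mm sentence still conflicts with the 5 mm limit. The hint about pathological nodes is never made an entry criterion. Cytology or histology shows whether a lesion is tumor; it sets no entry size.

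A reader might infer more than the documents support:

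- That any lesion of 10 to <20 mm is in dispute. It is not for spiral CT at 5 mm, and a subject changes status only if no other lesion is clearly measurable.
- That an unchanged normal-sized node produces a response. It contributes no fall in the sum. On the complete-response side, the nodal clause covers pathological nodes that shrink, and all other disease must also resolve.
- That each subject moved in or out of the set shifts the rate by 5 points. That figure applies only to rescoring one subject with 20 fixed.
- That eligibility or the primary endpoint is undermined. Entry requires measurable or evaluable disease, and Protocol Section 9.2.2 and SAP Section 7.2.1 assign efficacy endpoints, including PFS, to the Full Analysis Set. SAP Section 13 lists the PFS curve against the response set, but that is a separate discrepancy.

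**Conclusion.** The concern holds as an internal inconsistency plus a missing nodal rule. The size conflict covers lesions of 10 to <20 mm on non-spiral CT, MRI or calipers, if these count as conventional, and 10 to <16 mm at 8 mm slices. The nodal gap allows a 3 mm change in a normal-sized node to score as a partial response when that node is the only target, subject to confirmation.

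The size per affected subject is 1 to 5 points of response rate, under the assumption of 4 responders among 20. That is small beside an interval running from 5.7% to 43.7%, and these endpoints are secondary. The total effect cannot be stated, because the documents do not give the number of subjects whose lesions all fall in the disputed range or whose only target is a small node. The text should still be corrected, because Appendix E is what sites are told to follow and the correction is cheap.

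**What to change.** In Appendix E:

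- Keep one CT rule: 10 mm at slices of 5 mm or less, otherwise twice the slice thickness.
- Delete the clause that separates conventional techniques from spiral CT, and the sentence prescribing 5 to 8 mm reconstruction.
- State that nodes are measurable, and selectable as targets, by short axis only. Use the nodal threshold of the RECIST 1.1 guideline that the protocol cites, and in any case nothing below the 10 mm that Appendix E treats as normal. The guideline is not part of the documents reviewed, so its figure has to be taken from the source.

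Before database lock, check recorded baseline target lesions against the single rule. Recorded diameters alone will not be enough: Appendix E does not require measurements of non-target lesions, and the documents do not say that slice thickness or the long axis of nodes is recorded. Protocol Section 7 requires baseline scans to be stored and available for sponsor review, so use those where a diameter or slice thickness is missing. Fix the rule first and apply it to baseline scans, so that it is not chosen in the light of responses.

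The cost is a wording change and a small amount of checking. A few subjects may change response-set membership; none loses eligibility.

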**2 Abbreviations and Definitions**

AE	Adverse Event
CR	Complete Response (RECIST criteria)
CTCAE	Common Terminology Criteria for Adverse Events
DLT	Dose-Limiting Toxicity
ECG	Electrocardiogram
ECOG	Eastern Cooperative Oncology Group
eCRF	Electronic Case Report Form
ITT	Intent to Treat
MTD	Maximum Tolerated Dose
NE	Not evaluable (RECIST criteria)
PD	Progressive Disease (RECIST criteria)
PFS	Progression-Free Survival
PR	Partial Response (RECIST criteria)
RECIST	Response Evaluation Criteria in Solid Tumors
SAP	Statistical Analysis Plan
SD	Stable Disease (RECIST criteria)
SOC	System Organ Class
WHO Drug	World Health Organization Drug Dictionary Enhanced

### 3 Introduction

#### 3.1 Preface

This document describes the data analysis specifications for Rexahn Pharmaceuticals protocol RX-0201-P2-A-09 titled: "A Multicenter, Open-label, Phase 1b/2 Study to Evaluate the Safety and Efficacy of RX-0201 in Combination With Everolimus to Treat Subjects With Advanced Renal Cell Carcinoma". This version of the statistical analysis plan dated April 3, 2018 was prepared in accordance with the protocol RX-0201-P2-A-09 Amendment 04 dated March 8, 2017. Other related documents are the electronic case report form (eCRF) data definition fields and data set definitions.

#### 3.2 Purpose of the Analyses

The purpose of this Statistical Analysis Plan (SAP) is to provide a framework in which answers to the protocol objectives may be achieved in a statistically rigorous fashion using methods identified prior to database lock. Any deviations from these methods must be documented in the final clinical study report.

### 4 Study Objectives and Endpoints

#### 4.1 Study Objectives

##### Primary objective:

- To determine the maximum tolerated dose (MTD) of RX-0201, up to a target dose of 250 mg/m^2/day, when given in combination with everolimus (Stage 1)
- To determine progression-free survival in subjects with advanced renal cell carcinoma treated with the combination of RX-0201 and everolimus versus everolimus alone (Stage 2)

##### Secondary objective(s):

- To assess the pharmacokinetics of RX-0201 in combination with everolimus (Stage 1)
- To evaluate parameters of clinical benefit of RX-0201 in combination with everolimus versus everolimus alone as measured by duration of response, time to response, and response rate (Stage 2)
- To evaluate the safety and tolerability of RX-0201 in combination with everolimus versus everolimus alone (Stage 1 and Stage 2)

##### Exploratory objective:

- To investigate the effects of RX-0201 and everolimus on AKT pathway biomarkers, tumor apoptosis biomarkers and other biomarkers in blood or tumor samples (Stage 1 and Stage 2)
- To further evaluate the peak plasma concentration of RX-0201 at the target dose (Stage 2)

## 4.2 Endpoints

### Primary Endpoint:

- The incidence of adverse events and clinical laboratory abnormalities defined as dose-limiting toxicities (Stage 1)
- Progression-free survival at 4.5 months (Stage2)

### Secondary Endpoints:

- Pharmacokinetic profile of RX-0201 (Stage 1)
- Incidence of adverse events, changes in clinical laboratory tests and vital signs over time (Stage 1 and Stage 2)
- Tumor response rate, duration of response, time to response and response rates (Stage 2)

### Exploratory Endpoint:

- Blood levels of AKT pathway biomarkers, tumor apoptosis biomarkers or other biomarkers (Stage 1 and Stage 2)
- Plasma concentration of RX-0201 at the end of infusion (Stage 2)

## 4.3 Derived variables

### Subject Age

The subject's age will be calculated as the number of years from the subject's date of birth to his/her screening date: Age = ([Screening Date - Date of Birth] / 365.25).

### Baseline

The baseline value for any variable will be the value measured before first administration of study-specified treatment. For variables/assessments not scheduled to be performed on study day 1 or that are missing at baseline, the baseline value will be the value from the screening period measured closest to study day 1.

### Time from First Histopathological /Cytological Diagnosis to Screening Visit

Date of the first histopathological/cytological diagnosis will be captured in the EDC dataset. Date of screening visit will be captured in the Visit Date SAS dataset.

### Dose-Limiting Toxicity (DLT)

The definition of DLT is described in Section 6.5 of this SAP. Dose-limiting toxicity will be evaluated during Cycle 1 of treatment. For purposes of displaying DLTs on a per-subject and per-cohort basis,

the Electronic Data Capture (EDC) system will capture and identify whether or not a subject experiences a DLT in the AE dataset.

### **Maximum Tolerated Dose (MTD)**

The determination of Maximum Tolerated Dose (MTD) is described in Section 6.4 of this SAP.

